6.1.4 Other Efficacy Variables

Not applicable

6.2 Safety Variables

Safety will be assessed by evaluation of the following variables:

- Treatment-emergent adverse events (TEAEs; frequency, severity, seriousness, and relationship to study drug).

TEAE is defined as an AE observed on or after the day of starting the administration of the test drug/comparative drug. If a subject experiences an event both during the pre-investigational period and during the investigational period, the event will be considered as TEAE only if it has worsened in severity (i.e., it is reported with a new start date). All AEs collected that begin within seven days after taking the last dose of study drug will also be counted as TEAE. Based on conservative rule, all AEs that could not be determined as started before transplant or after seven days of the last study dose will be assumed to be TEAEs.

A drug-related TEAE is defined as any TEAE with at least a possible relationship to study treatment, as assessed by the investigator.

For TEAE (and serious TEAE), the exposure-adjusted incidence rate (EAIR) will be calculated using following formula:

$$\text{EAIR (\%)} = 100 * n / \text{sum of exposure}$$

In the formula, n is the number of subjects with an event (e.g. one SOC/PT category). Sum of exposure is the total exposure time of all subjects in the group. For subject with one event, exposure time = time from transplant to the event; for subject with multiple events, exposure time = time from transplant to the earliest event; for subject with no event, exposure time = time from transplant to end of study. Because of the large sample size of the study, time unit is set to Year.

- The safety endpoint for AEs will be the incidence of each type of AE based on system organ class and using the preferred term from the Medical Dictionary for Regulatory Activities (MedDRA) version 20.1.
- Clinical laboratory variables (hematology, biochemistry including liver enzymes and total bilirubin, urinalysis, coagulation, and tacrolimus trough levels).

6.3 Pharmacokinetic Variables

Not applicable

6.4 Pharmacodynamic Variables

Not applicable

6.5 Other Variables

Baseline

Baseline renal function (serum creatinine, eGFR) will be defined as the value measured at the Day 30 visit. For all other data, the baseline value will be defined as the last observation collected prior to or at the time of reperfusion of the transplanted kidney.

Extended Criteria Donor (ECD)

The donor characteristics that define an ECD kidney include age \geq 60 years, or age 50-59 years plus two of the following: cerebrovascular accident as the cause of death, preexisting hypertension, or terminal serum creatinine greater than 1.5 mg/dl.

Study Days

For the purpose of analyzing time to event endpoints, the time-in-study for each subject will be measured relative to Day 0, the day of transplantation; defined as the date in which reperfusion to the transplanted organ is established. From this starting point, the day of reperfusion will be considered the first day in study for each subject for analysis and the study days will be calculated as:

Date of event - Date of reperfusion

Study Treatment Dose Increased, Decreased, Interrupted, or Treatment Arm Switched

During the whole study treatment period, a subject is considered as:

- Dose Increased – at least one treatment record has higher dose than that of at least one previous record
- Dose Decreased – at least one treatment record has lower dose than that of at least one previous record
- Dose Interrupted – at least one gap (i.e. non-treated days between two records) is \geq 7 days
- Arm Switched – at least one treatment record with non-assigned treatment (i.e. not the randomized treatment group)

Time on Treatment (days)

For each subject, the length of time from first dose of study medication to date of discontinuation from study treatment will be calculated in days, using the following formula: ('Date last dose of study drug' - 'Date first dose') + 1

Actual Treatment Exposure (days)

For each subject, Actual Treatment Exposure (days) will be the sum of treatment days of all treatment records = Sum of all treatment records' ('Stop Date' – 'Start Date' + 1), where the treatment record must have Dose > 0.

Average Daily Dose (mg/day)

Average Daily Dose = Total dose (mg) of study drug / Actual Treatment Exposure (day).

Inpatient Variability (IPV) of Tacrolimus Trough Level

If the subject had at least three non-missing tacrolimus trough concentration assessments between Week 6 (Day 42) and Day 365, the IPV will be estimated from CV%, geometric CV%, and SD:

CV% = $(\sigma/\mu) \times 100$, where σ is standard deviation and μ is mean of the tacrolimus trough levels

Geometric CV% = $\sqrt{\exp(\sigma_{\log}^2)-1} \times 100$, where σ_{\log} is the standard deviation of log-transformed tacrolimus concentration value.

SD = standard deviation

Above three IPV's will also be calculated from dose-adjusted tacrolimus concentration:

Dose-adjusted Tacrolimus Concentration = Tacrolimus Concentration / Tacrolimus Dose of that Day.

Switching of Tacrolimus Manufacturer

The study medication of the BID Immediate-release tacrolimus can be from different manufacturers. A manufacturer switch is counted if the manufacturer(s) of record (based on NDC codes) at one dispensing date are not completely same as those of the previous dispensing.

Compliance

The two common measures of medication adherence using refill data are the medication possession ratio (MPR) and proportion of days covered (PDC). Although the MPR has been used to define medication adherence in kidney transplantation, the PDC seems to be the estimator of choice for CMS and pharmacies. This is due to the fact that the PDC estimator is considered a more conservative measure of refill record-based adherence.

PDC is the percentage of days covered with medication, calculated based on dispensing days from the pharmacy, as shown in the following formula:

$$PDC = \left(\frac{\text{Number of days in period "covered"}}{\text{Number of days in period}} \right) \times 100\%$$

PDC threshold for compliance is typically set at 80% of days covered. This means that someone missing 5 or fewer days' worth of medication in an average month is considered compliant.

Steps to calculate individual PDC based on dispensing data are provided below:

- Step 1: Determine subject's measurement period, defined as the index prescription date until graft loss, death or end of 12-month follow-up period. Index prescription date can be the first fill date after discharge from the hospital for kidney transplantation.
- Step 2: Within the measurement period, count the days the subject was covered (2-daily, immediate release) based on the prescription fill date and days of supply. If prescriptions for the same drug overlap, then adjust the prescription start date to be the day after the previous fill has ended.
- Step 3: Divide the number of covered days found in Step 2 by the number of days found in Step 1. Multiply this number by 100 to obtain the PDC (as a percentage) for each subject.
- Step 4: Count the number of subjects who had a PDC greater than 80% and then divide by the total number of eligible subject.

MPR is a ratio between number of days of medication supply and number of days in the refill interval. MPR is calculated as:

$$\text{MPR} = \left(\frac{\text{Total number of days of medication supplied}}{\text{Number of days in period}} \right) \times 100\%$$

The number of days in period (e.g., 1 year) is the sum of the number of days from first dispensing (ie., first fill date after discharge from the hospital for kidney transplantation) up to the date of last dispensation plus the number of days' supply obtained at the last dispensation (e.g., 30 days). Any prescription days' supply that spans the 1-year observation period will be truncated at 365 days. MPR threshold for compliance is typically set at 80%.

For this study, the study drug dispense data is only available for the BID Immediate-Release Tacrolimus group. PDC, MPR, and their compliance rates can only be calculated for that treatment group.

Previous and concomitant medication

Previous medication is defined as medications which started and stopped prior to transplant.

Concomitant medication is defined as medications with at least one dose taken between the date of transplant (inclusive) and the date of last dose (inclusive) of study drug.

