3 STUDY POPULATION

3.1 Selection of Study Population

This study will enroll 550 living or deceased donor kidney transplant recipients, 16 to 70 years of age. Patients will be screened and randomized 1:1 prior to surgery to receive, twice daily, immediate-release tacrolimus or Astagraf XL as a component of a standard immunosuppression maintenance regimen also consisting of corticosteroids (complete steroid avoidance not allowed – steroid taper and withdrawal permitted if given per institutional protocol) and MMF (or Myfortic equivalent) (see Section 4.5 for randomization details). After discharge from the hospital, patients randomized to receive twice-daily immediate-release tacrolimus will receive study-provided vouchers and will be permitted to receive any immediate-release tacrolimus product available to them through normal dispensing mechanisms. Patients randomized to receive Astagraf XL will receive this treatment for the duration of the study and will not be permitted to use other extended-release tacrolimus formulations.

Upon request from the investigator, the Sponsor's medical monitor will consider requests for patient re-screenings on a case-by-case basis.

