4.1.2 Comparative Drug(s)

Tacrolimus, immediate-release, oral; 0.5 mg, 1 mg, 5 mg capsules to be obtained by the transplanting center during a participant’s inpatient stay, and by the patients themselves, thereafter, at retail pharmacies via a study-provided voucher for the study duration of up to 24 months.

IF medically indicated, subjects randomized to the immediate release tacrolimus treatment arm who are unable to tolerate oral administration may be administered tacrolimus via either IV solution, (**Prograf** solution for intravenous use) administered as a 24-hour continuous infusion, or via NGT for no more than seven consecutive days. Dosing via these routes should be discontinued as soon as the subject can tolerate oral administration, and may not exceed a period of seven consecutive days. Additionally, a subject may not receive more than

seven days of combined NGT and IV administration in cases where a subject is switched from one therapy to another. Intravenous tacrolimus will not be provided by the Sponsor.

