5.1.4 Treatment Compliance

Study subjects should be counseled on the need to exhibit 100% compliance with their medication regimen in a manner that reflects a center's own standard of care. As this study is designed to assess the real-world impact of either once-daily Astagraf XL or a twice daily tacrolimus regimen, investigators or their designee should not change how they counsel patients on compliance based on their patient's randomization status or participation in ASTOUND.

Astagraf XL will be monitored by the accounting of unused medication returned by the subject at quarterly visits. Patients receiving immediate-release tacrolimus will be monitored by a third party vendor (via voucher system). Manufacturer, dose, number of pills dispensed, and the date of prescription refills will be captured using a voucher system with a built-in reporting mechanism.

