3.1.2 Secondary Objectives

The secondary objectives of the study, as stated in the protocol, have been further clarified and adjusted to more closely address the research questions and in consideration of data availability. They are to:

- Assess the risk factors for each of the following outcomes: Interstitial Fibrosis and Tubular Atrophy (IFTA), IFTA and Inflammation, biopsy-proven acute rejection (BPAR), the four-part traditional composite endpoint, early mycophenolate mofetil (MMF) interruption/discontinuation, and estimated glomerular filtration rate (eGFR) status based on three thresholds 30, 40, and 50 at one year.
- Assess and compare, between treatment groups, the association/correlation of the appearance of DSA with the development of IA on molecular profiling at one year.
- Assess and compare, between treatment groups, the incidence of each of the following, occurring over the course of one year : De novo DSA, C1q-binding DSA, DSA IgG₃ isotype, IA, transplant glomerulopathy (TG), select BANFF histology grades (acute and chronic forms of antibody-mediated rejection (ABMR), acute and chronic active T-cell mediated rejection (TCMR), borderline changes, and IFTA), graft loss, mortality, and BPAR.
- Compare, between treatment groups, the incidence of various thresholds of eGFR (less than 30, 40, 50 mL/min/1.73 m²) at Day 365 visit and a five-point decline from Day 30 to Day 365).
- Summarize the distribution of ordinal categories of antibody strength (weak, moderate, strong) between treatment groups across the 1-year study time course.
- Summarize maximum Mean Fluorescence Intensity (MFI) scores by treatment group across the duration of the study.
- Examine histopathology in cases where biopsies were taken for maintenance (up to fourteen months) between treatment groups. In cases where biopsies were performed for cause, they will be examined separately.
- Summarize tacrolimus manufacturer and the number of switches between immediate-release tacrolimus products by the occurrence of study composite endpoint.
- Summarize tacrolimus manufacturer and the number of switches by the status of renal dysfunction.
- Summarize adverse events (AEs) between treatment groups.

- Summarize the absolute and percent changes in eGFR over the study duration beginning from 30 days post-transplant between groups, and in subjects who develop DSA or IA.

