7.3 Study Drugs

7.3.1 Exposure

The following information on drug exposure according to the details in Section 6.5 will be presented for each treatment group for the SAF:

- Descriptive statistics for cumulative amount of the drug that a subject was exposed to and average daily dose; and
- Number and percent of subjects with dose increases, decreases, or interruption by treatment group.

Duration of exposure will be summarized in two ways.

- Descriptive statistics will be presented by treatment group.
- Exposure time will be categorized according to the following categories by treatment group:
 - less than 7 days
 - at least 7 days, less than 14 days
 - at least 14 days, less than 28 days
 - at least 28 days, less than 42 days
 - at least 42 days, less than 60 days
 - at least 60 days, less than 91 days
 - at least 91 days, less than 182 days
 - at least 182 days, less than 364 days
 - 364 days or more
 - Unknown.

Counts and percentages of subjects in each of these categories will be summarized for each treatment group for the SAF.

Additionally, descriptive statistics (counts and percentages) will be used to assess for the BID Immediate-release Tacrolimus treatment group for the SAF the distribution of use for the different tacrolimus formulations in the study (i.e., generic formulations of immediate release tacrolimus) and the frequency of manufacturer switching for the study.

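### The manufacturer-switch rule ignores capsule strength, so a control patient whose strengths come from different manufacturers and are not always filled together is scored as switching when no strength changed manufacturer

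*SAP*

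**What the plan says.** SAP 6.5, under the definition of switching, notes that "The study medication of the BID Immediate-release tacrolimus can be from different manufacturers". It then counts a switch if the "manufacturer(s) of record (based on NDC codes) at one dispensing date are not completely same as those of the previous dispensing". There is no condition on strength, on supply still in hand, or on which item was refilled.

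Protocol 4.1.2 lists the control drug as "Tacrolimus, immediate-release, oral; 0.5 mg, 1 mg, 5 mg capsules to be obtained by the transplanting center" and later, after discharge, by patients at retail pharmacies. Protocol 3.1 says that these patients "will be permitted to receive any immediate-release tacrolimus product available to them through normal dispensing mechanisms". Protocol 5.1.4 describes the data: "Manufacturer, dose, number of pills dispensed, and the date of prescription refills will be captured using a voucher system".

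The count is used in three places in the SAP. Two are secondary objectives in 3.1.2: "Summarize tacrolimus manufacturer and the number of switches between immediate-release tacrolimus products by the occurrence of study composite endpoint" and "Summarize tacrolimus manufacturer and the number of switches by the status of renal dysfunction". The third is the exposure summary in 7.3.1, which reports "the frequency of manufacturer switching for the study" for the immediate-release arm.

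**The concern.** The objective in SAP 3.1.2 is about switches between products. A switch in that sense means that something the patient takes has been replaced by another manufacturer's version. The rule in SAP 6.5 measures something else: whether the list of manufacturers on today's dispensing record equals the list on the last one. The two agree for a patient on one strength. They can part company for a patient on several strengths from several manufacturers, because a dispensing record shows only what was filled that day and not everything the patient is taking.

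What is at stake is the meaning of two secondary-objective tables and one exposure table. If the count partly reflects refill timing, neither the frequency of switching nor its cross-tabulation with the composite endpoint and renal dysfunction can be read at face value.

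**Working it through.** The documents give no figure for the switch count, so there is nothing to reproduce. The check applies the SAP 6.5 rule literally to constructed fill histories.

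**Inputs from the documents**
- Rule: compare the set of manufacturers at each dispensing date with the set at the previous one; any difference is one switch (SAP 6.5).
- Strengths available: 0.5, 1 and 5 mg (Protocol 4.1.2).
- Manufacturer: any, and none is required to be common to all strengths (Protocol 3.1).

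**Assumptions**
- 12 months of follow-up with 30-day fills unless stated.
- Two manufacturers, A and B.

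**Formulas**
- SAP count = number of consecutive date pairs in which the manufacturer sets differ.
- Same-strength count = number of consecutive fills of one strength in which the manufacturer differs, summed over strengths.
- New-manufacturer flag = number of first fills of a new strength whose manufacturer the patient was not already using. Fills that make up the starting regimen set the baseline and are not flagged.

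| History | Date pairs compared | SAP 6.5 count | Same-strength count | New-manufacturer flag |
|---|---|---|---|---|
| One strength, A throughout | 11 | 0 | 0 | 0 |
| Two strengths, both A, staggered dates | 23 | 0 | 0 | 0 |
| Two strengths, A and B, filled together every time | 11 | 0 | 0 | 0 |
| Two strengths, A and B, staggered dates | 23 | 23 | 0 | 0 |
| A every 30 days, B every 90 days, same start | 11 | 7 | 0 | 0 |
| A throughout, second strength from B for 3 months | 11 | 2 | 0 | 1 |
| 1 mg from A replaced by 5 mg from B | 11 | 1 | 0 | 1 |
| One strength, A to B | 11 | 1 | 1 | 0 |
| Manufacturers swap between two strengths on one date | 11 | 0 | 2 | 0 |

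**How the main rows arise**
- Staggered A and B: 12 + 12 = 24 dispensing dates, so 24 − 1 = 23 pairs. The record reads {A}, {B}, {A}, {B} and every pair differs. No product changed.
- A every 30 days, B every 90: B appears on 4 of 12 dates. The first is the starting date and produces one change, when B is next absent. The other three each produce two, on reappearing and on being absent again: 1 + 3 × 2 = 7. Again no product changed.
- Second strength from B for 3 months: one change when B appears and one when it goes, 2 in all. The appearance is first exposure to B. The disappearance is not a change of manufacturer for anything still being taken.
- Swap: the set is {A, B} before and after, so the rule sees nothing, while both strengths changed manufacturer.

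The rule is therefore right for a single strength and harmless when one manufacturer supplies everything or all strengths are filled together. It miscounts, in either direction, for patients who hold strengths from more than one manufacturer.

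**The case against.** The best defence has three parts.

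First, the SAP clearly foresaw several manufacturers at one dispensing, and treating a move from A alone to A plus B as a switch is a defensible definition, because the patient has begun taking B's product. This stands for an added strength from a new manufacturer, and for a full move from 1 mg A to 5 mg B. It does not cover the staggered or unequal-interval refills, where nothing the patient takes has changed.

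Second, the consequence is small. SAP 3.1.2 and 7.3.1 only summarize switches. The risk-factor lists in SAP 7.4.2 omit switching, and the separate control-arm models there add manufacturer, not the number of switches. Protocol 7.6 foresees comparing switchers with non-switchers on tacrolimus concentration, but the trough analyses in SAP 7.3.3 contain no such comparison. This stands.

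Third, the frequency is unknown and may be zero. This stands too.

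Two stronger readings are tempting and should be resisted. A reader might infer that any change of strength is counted as a switch. It is not: the rule compares manufacturers, and strength changes within one manufacturer score 0. A reader might also infer that any association between switching and poor outcomes would come only from dose changes. The documents do not support that. The large false counts arise in patients on a stable regimen, the dose-change histories add only 1 or 2, and no document quantifies a link between false switches and outcome. The share of control doses that need several strengths cannot be estimated either, because the fewest-capsules instruction in Protocol 5.1.1 is written for Astagraf XL.

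**Conclusion.** The point holds for control patients whose strengths come from different manufacturers and are not always filled on the same date. For them the SAP 6.5 rule counts refill timing as switching, and it can also miss real changes when manufacturers swap between strengths. The illustrative false count is 0 to 23 a year. That range rests on assumed fill intervals and two manufacturers and is not an estimate of what the trial will show. The error is zero with a single manufacturer or joint fills.

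The effect is confined to the control-arm descriptive switch summaries in SAP 3.1.2 and 7.3.1. The primary analysis and the between-arm comparisons are untouched. It is still worth correcting, because the variable serves two secondary objectives and does not measure what they name.

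**What to change.** Reword the definition in SAP 6.5 along these lines:

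- Compare the manufacturer at each fill with the manufacturer at the previous fill of the same capsule strength, and count a switch if they differ.
- Do not count the mere absence of a strength at a fill.
- Count the first fill of a new strength as a switch only if its manufacturer differs from every manufacturer the patient was already using, and flag these cases separately from same-strength switches.
- State that the fills making up the starting regimen define the baseline. Otherwise a staggered start with A and B would produce one flagged case.

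Report the same-strength count and the flagged cases side by side in the SAP 3.1.2 and 7.3.1 tables.

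The cost is a few sentences and a grouping by strength in the derivation. No new data should be needed: Protocol 5.1.4 lists manufacturer, dose, pill count and refill date as captured, and SAP 6.5 already uses NDC codes. The one thing to confirm is that the voucher file identifies the strength of each fill, since the documents name the NDC code only as the source of the manufacturer.

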12. After discharge from the hospital, patients randomized to receive twice daily immediate-release tacrolimus will receive study-provided vouchers and will be permitted to receive any immediate-release tacrolimus product available to them through normal dispensing mechanisms. At the final study visit, subjects will return unused vouchers; following the final study visit, vouchers previously provided to the subjects will be deactivated to prevent additional use. Additional vouchers will not be provided to subjects at the final study visit.
13. Recording of hematology, serum chemistries, urinalysis (including urine protein), tacrolimus trough concentrations, HgA1c, and whole blood tacrolimus concentrations obtained per SOC. See Section 5.4.3 for the components of the routine clinical labs that will be recorded. For all labs except whole blood tacrolimus concentrations and creatinine, only those labs obtained closest to targeted date of visit need to be recorded. For the Day 0 visit, pre-transplant labs should be recorded. For whole blood tacrolimus concentrations, at the Day 0 and Day 30 visits, only the concentration obtained closest to the targeted date of visit needs to be recorded. For the 90, 180, 270, and 365 day visits, all available outpatient tacrolimus concentration assessments done (per SOC) and available in the centralized medical records since the previous study visit should be recorded. For creatinine assessments, the assessment done closest to the targeted

- date of visit (obtained per SOC) as well as an additional assessment done at least one month prior to that assessment (if obtained per SOC) will be recorded on the eCRF.
14. For visits following day 365, only serum creatinine levels, urinary protein, and tacrolimus trough concentrations obtained as part of SOC should be recorded. For all labs except creatinine, only labs obtained closest to targeted date of visit need to be recorded. For creatinine assessments, the assessment done closest to the targeted date of visit (obtained per SOC) as well as an additional assessment done at least one month prior to that assessment (if obtained per SOC) will be recorded on the eCRF.

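### The PDC period has no end point for leaving the study, so most control subjects who leave early or mid-year are scored non-compliant however well they took tacrolimus

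*SAP*

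**What the plan says.** SAP 6.5 (Compliance) builds PDC in four steps.

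- **Step 1, denominator.** The period is "defined as the index prescription date until graft loss, death or end of 12-month follow-up period". On its start: "Index prescription date can be the first fill date after discharge from the hospital for kidney transplantation".
- **Step 2, numerator.** Covered days are counted "based on the prescription fill date and days of supply".
- **Step 4, compliance rate.** "Count the number of subjects who had a PDC greater than 80% and then divide by the total number of eligible subject". The SAP does not say who is eligible.

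The fill data come from one source. Protocol 5.1.4 says that manufacturer, dose, pill count and "the date of prescription refills will be captured using a voucher system with a built-in reporting mechanism". Footnote 12 of the schedule of assessments adds that after the final study visit "vouchers previously provided to the subjects will be deactivated to prevent additional use". Protocol 6.1 says that, apart from adverse event follow-up, no further clinical information is collected after discontinuation.

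MPR, in the same SAP section, runs from the first dispensing to the last one plus its days of supply. SAP 7.3.2 reports PDC and MPR descriptively for the immediate-release arm only and drops all planned between-arm comparisons of compliance.

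**The concern.** Protocol 6.1 lists many ways to leave the study. Only graft loss and death also end the PDC period. A subject who withdraws consent, is lost to follow-up, is converted to the other arm or stops for toxicity leaves with the denominator still running, while the only source of covered days has closed. Such a subject may go on taking tacrolimus perfectly outside the study and still be scored as uncovered for the rest of the year. For these subjects PDC measures retention more than adherence.

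The error has one direction: it can only lower PDC. Adherence is part of the trial's rationale (Protocol 1.1), and no compliance figure will exist for Astagraf XL. An understated figure for twice-daily dosing would have no counterpart against which to judge it. For the same subject, PDC and MPR would also differ for a reason unrelated to drug taking.

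**Working it through.** **Check of the plan's own figure.** The SAP explains its threshold thus: "someone missing 5 or fewer days' worth of medication in an average month is considered compliant". In a 30-day month, 5 missed days give 25/30 = 83.3%, which passes. Six give 24/30 = 80.0%, which is not greater than 80%. The statement reproduces. (With 365/12 = 30.4 days, 6 missed days give 80.3% and would pass.)

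**Inputs**
- From the documents: period end, numerator and strict cut above 80% (SAP 6.5); 275 subjects per group and 20% dropout allowance (SAP 4), so 0.20 × 275 = 55 control subjects.
- Assumed: the subject fills perfectly until leaving on day t; the index fill is on day 0; the period runs to day 365; s days of supply are in hand at exit and count as covered; no exit is by graft loss or death; exit times are uniform over the year.

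**One leaver.** PDC = min(1, (t + s)/365). With s = 0:

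| Leaves on day | PDC |
|---|---|
| 90 | 24.7% |
| 180 | 49.3% |
| 270 | 74.0% |
| 293 | 80.3% |
| 330 | 90.4% |

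**Where the cut falls.** PDC exceeds 80% when t > 0.80 × 365 − s = 292 − s. The last failing day is 292, 262 or 202 for s = 0, 30 or 90. Moving the index fill to day 5 or 14 shifts these limits by at most 3 days. With 95% coverage before exit and s = 0, the limit is 0.80/0.95 × 365, or day 307.

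**The arm.** Share of leavers failing = (292 − s)/365. Reported rate for an arm fully adherent while in the study = 1 − dropout × share.

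| Supply in hand | Share of leavers failing | Of 55 leavers | Rate, 20% dropout | Rate, 10% dropout |
|---|---|---|---|---|
| 0 days | 292/365 = 80.0% | 44.0 | 84.0% | 92.0% |
| 30 days | 262/365 = 71.8% | 39.5 | 85.6% | 92.8% |
| 90 days | 202/365 = 55.3% | 30.4 | 88.9% | 94.5% |

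**After the change.** If the period also ends on day t, a perfectly adherent leaver has t covered days out of t. PDC is then 100% for any exit day, and the arm's rate is 100% in every cell.

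**The case against.** The strongest objections are these.

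- **The text may not mean this.** The end of 12-month follow-up could be the end of each subject's own follow-up, and eligible could exclude leavers. The first reading is strained: if own follow-up were meant, graft loss and death, both study exits, would not need separate mention. The second cannot be ruled out, which is a reason to define the term.
- **Voucher deactivation at early exit is inferred.** It is tied to the final study visit, and the schedule shows no early-termination visit. This stands as a caveat, but no other source of fills is planned.
- **The consequence is small.** This stands. PDC enters neither the primary model (SAP 7.4.1.1) nor the listed risk factors (SAP 7.4.2).
- **Some leavers really are non-adherent.** Gross non-compliance is a discontinuation reason in Protocol 6.1. The illustration isolates the artefact and does not predict the observed rate.

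A reader might also go further than the documents allow:

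- **That every early leaver is scored non-adherent.** Graft loss and death end the period, late leavers with good coverage still pass, and a subject with no outpatient fill has no index date and so no PDC.
- **That PDC is the only adherence figure.** MPR is reported beside it.
- **That 16% of the arm will be misclassified.** That is the corner with 20% dropout and no supply in hand (0.20 × 80%). The 20% allowance was set for a study of up to two years.

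**Conclusion.** The point holds in a limited form. As written, the PDC rule counts days after study exit as uncovered when no fill could be recorded, and most subjects who leave early or mid-year for reasons other than graft loss or death would be scored non-compliant. Under the stated assumptions, 55% to 80% of such leavers fail, and a fully adherent arm is reported as about 84% to 94.5% compliant instead of 100%. The range depends on the dropout rate within the year, exit times and supply in hand, none of which the documents give for the control arm's first year. The effect is confined to one descriptive, control-arm summary and alters no test or treatment comparison. It deserves correction because it always lowers the figure and is easily removed.

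**What to change.** In SAP 6.5 Step 1, end the PDC period at the earliest of graft loss, death, study discontinuation (the date on which voucher fill capture ends) or day 365. In Step 4, define eligible, for example as control subjects with at least one outpatient fill.

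Leave the MPR period alone, since its end is already stated. Do not end the PDC period at the last dose for subjects who remain in the study: that would hide those who stop taking tacrolimus while under observation, and non-persistence should still count.

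The cost is a line or two of SAP text, using dates the trial already holds. The small downside is that PDC would describe adherence only while in the study, so it should be presented with the disposition table of SAP 7.2.1.
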